#### **6.11.4.4 Change from baseline in serum creatinine**

Serum creatinine data will be available in lab data. The response variable, change from baseline in serum creatinine, will be summarized at Weeks 2, 4, 8, 12, 16, 20, 24, 30, 36, 42, 48 and 52 (Table 14.2.9). Listings of this endpoint will be provided with lab data. Baseline is calculated as defined in Section 6.2.2

#### **6.11.4.5 Change from baseline in urine protein**

Urine protein will also be collected from lab data. The response variable, change from baseline in urine protein will be summarized at Weeks 2, 4, 8, 12, 16, 20, 24, 30, 36, 42, 48 and 52 (Table 14.2.10). Listings of this endpoint will be provided with lab data. Baseline is calculated as defined in Section 6.2.2.

#### **6.11.4.6 Change from baseline in eGFR**

Estimated glomerular filtration rate (eGFR) will be measured at all visits except Visit 2. The response variable change from baseline in eGFR will be summarized at Weeks 2, 4, 8, 12, 16, 20, 24, 30, 36, 42, 48 and 52 (Table 14.2.11.1). Baseline is calculated as defined in Section 6.2.2.

These change from baseline tables will be produced using both corrected and raw eGFR values.

Listings of this endpoint will be provided with lab data.

#### **6.11.4.7 Change from baseline in immunology parameters (C3, C4, and dsDNA) at Weeks 24 and 52**

Each of the Lupus Markers: Complement 3, (C3), Complement 4 (C4), and dsDNA will be analyzed separately at weeks 24 and 52. C3, C4, and dsDNA is measured at screening, Week 24, and Week 52 (Table 14.2.12). Listings of this endpoint will be provided with lab data.

#### 6.11.4.8 Renal response with low-dose steroids at weeks 24 and 52

Renal response with low-dose steroids is defined as renal response in the presence of corticosteroids of  $\leq 2.5$  mg/day between Weeks 16 to 24 (for Week 24 endpoint) and Weeks 44 to 52 (for Week 52 endpoint). This endpoint will be analyzed in a similar manner as that described in Section 6.11.2 (Table 14.2.13).

#### 6.11.4.9 Change from baseline in HRQoL at Weeks 12, 24, and 52

SF-36 and LupusPRO HRQoL will be answered by the subject at Baseline, Week 12, 24 and 52. Listings of observed and change from baseline HRQoL scores will be presented. A baseline HRQoL value is defined as the last HRQoL value prior to the first dose on Day 1. HRQoL total scores will be analyzed as a change from baseline endpoints described above for the ITT population.

##### 6.11.4.9.1 Change from baseline in Short Form Health Survey (SF-36)

The SF-36 HRQoL assessment is a 36-question subject HRQoL questionnaire. The SF-36 responses will be weighted as indicated in Table 6.2.

**Table 6.2 SF-36 responses and weighting**

Item number	Original Response	Weight
1, 2, 20, 22, 34, 36	1 →	100
	2 →	75
	3 →	50
	4 →	25
	5 →	0
3, 4, 5, 6, 7, 8, 9, 10, 11, 12	1 →	0
	2 →	50
	3 →	100
13, 14, 15, 16, 17, 18, 19	1 →	0
	2 →	100
21, 23, 26, 27, 30	1 →	100
	2 →	80
	3 →	60
	4 →	40

Item number	Original Response	Weight
	5 →	20
	6 →	0
24, 25, 28, 29, 31	1 →	0
	2 →	20
	3 →	40
	4 →	60
	5 →	80
	6 →	100
32, 33, 35	1 →	0
	2 →	25
	3 →	50
	4 →	75
	5 →	100

These items will be further grouped into the following scales as shown in [Table 6.3](#).

**Table 6.3 SF-36 Scales**

Scales	Number of items	Mean of Items
Physical functioning	10	3, 4, 5, 6, 7, 8, 9, 10, 11, 12
Role limitations due to physical health	4	13, 14, 15, 16
Role limitations due to emotional problems	3	17, 18, 19
Energy/fatigue	4	23, 27, 29, 31
Emotional well-being	5	24, 25, 26, 28, 30
Social functioning	2	20, 32
Pain	2	21, 22
General health	5	1, 33, 34, 35, 36
Total mean score	36	All 36 items

Each scale will be calculated for each subject by taking the mean of its corresponding item. The observed and change from baseline scales values will be summarized by visit and treatment arm. Only the scales (Physical functioning, Role limitations due to physical health, Role limitations due to emotional problems, Energy/fatigue, Emotional well-being, Social functioning, Pain, General health, Total mean score) will be summarized (Table 14.2.14.1). An MMRM model of the change from baseline in total mean score will also be presented. The individual items and scales will be listed.

#### 6.11.4.9.2 Change from baseline in LupusPRO(v1.7)

The LupusPRO (v1.7) is a 43-question subject HRQoL questionnaire specific for lupus. The questionnaire will be grouped into the following domains:

**Table 6.4 LupusPRO questionnaire**

Items	Construct	Domain	Reverse Coding needed?
1-3	HRQOL	Lupus Symptoms	Yes
4-5	HRQOL	Cognition	Yes
6-7	HRQOL	Lupus Medications	Yes
8-9	HRQOL	Procreation	Yes
10-14	HRQOL	Physical Health	Yes
15-19	HRQOL	Pain Vitality	Yes
20-25	HRQOL	Emotional Health	Yes
26-30	HRQOL	Body Image	Yes
31-34	N- HRQOL	Desires-Goals	Yes
35-36	N- HRQOL	Social support	No
37-39	N- HRQOL	Coping	No
40-43	N- HRQOL	Satisfaction with care	No

The LupusPRO® has 5 point Likert response format, where 0= None of the time/not applicable, 1= A little of the time, 2= Some of the time, 3=Most of the time, 4= All of the time, 5= Not applicable (recode as 0 for scoring). Reverse scoring for some items is required (as above). There are 12 observed domains. Item scores are totaled for each domain item and the mean domain score is obtained by dividing the total score by the number of items in that domain. The mean raw domain score is transformed to scores ranging from 0 (worst QOL) to 100 (best QOL) by dividing by 4 (the number of Likert responses {5 responses} minus 1) and then multiplying by 100, as below:  $(\text{Mean raw domain score}/4) \times 100 = \text{Transformed score for the domain}$ . Transformed domain scores will be obtainable when at least 50% of the items are answered. Total HRQOL and N-HRQOL scores are obtained by averaging the transformed domain scores within each construct. Observed and change from baseline values will be summarized by visit and treatment (Table 14.2.15). An

MMRM model of the change from baseline in HRQOL and N-HRQOL score will also be presented. A listing of the 43 items, the domains, and the total HRQOL and total N-HRQOL will be provided.

#### **6.11.4.10 Change from baseline in the SELENA-SLEDAI Index score at Weeks 24 and 52**

The SELENA-SLEDAI assesses disease activity within the last 10 days. Twenty-four items are scored for 9 organ systems, and summed to a maximum of 105 points. A score of 6 is considered clinically significant. Assessments for SELENA-SLEDAI will be conducted at baseline, Week 24, and Week 52. A patient's SELENA-SLEDAI total score at a given visit is the sum of the weighted scores of all marked SLE-related descriptors. A total score can fall between 0 and 105, with a higher score representing a more significant degree of disease activity. Change from baseline in SELENA-SLEDAI total score will be the response variable in the MMRM model (Table 14.2.16). The scores of the individual SELENA-SLEDAI items and the total score of each subject will be listed.

#### **6.11.4.11 Health Resource Utilization at Weeks 24 and 52**

Information on healthcare resource utilization will be collected at time points: baseline (Day 1), Week 24, and Week 52, and documented in the EDC system. This information will be collected via interview of the subject by the study staff and entered into the EDC system. General information collected may include:

[figure not shown]
- Type of insurance coverage (private, NHS, other)
- Number of visits to ANY health care professionals (HCP), other than study doctor
- Types of HCP visited (specialists versus primary care)
- Time spent on visits (in minutes)
- Diagnostic tests performed (Yes/No)
- Time (in minutes) spent by caregivers assisting patient with HCP visits
- Prescriptions issued (Yes/No), filled (Yes/No)
- Community services used (Yes/No)

Each item in the Health Resource Utilization questionnaire will be summarized for baseline (Day 1), Week 24, and Week 52. All the items will also be listed at subject level.

### 6.11.5 Multiplicity

An overall type 1 (false-positive) error rate of 5% for the efficacy endpoints will be maintained so that no statistical significance for the key secondary efficacy endpoints will be claimed unless the principal analysis of the primary efficacy endpoint using the ITT population is statistically significant at the 5% level. The Hochberg step-up procedure [2] will be used to adjust for multiple comparisons amongst key secondary endpoints and maintain the overall type 1 error rate. Data from all analyses, regardless of the level of significance, will be presented for review.

**Figure 6.1 Hochberg procedure**

#### 6.11.5.1 First Overall Comparison -Voclosporin 23.7 mg BID versus Placebo for Primary Efficacy Endpoint.

The comparison of voclosporin 23.7 mg BID versus Placebo in the primary efficacy endpoint, renal response at Week 52, will be tested first at a 0.05 significance level. If the p-value for this comparison  $\geq 0.05$ , then testing will stop. Otherwise, the comparisons of voclosporin 23.7 mg BID versus Placebo for the Key secondary efficacy endpoints will be tested using the Hochberg procedure.

#### **6.11.5.2 Secondary Comparisons - Voclosporin 23.7 mg BID versus Placebo for Secondary Efficacy Endpoint.**

The key secondary endpoints are:

- Time to UPCR  $\leq 0.5$  mg/mg
- Partial renal response at Week 52
- Partial renal response at Week 24
- Time to 50% reduction from baseline in UPCR
- Renal response at Week 24 (Adjudicated)

If the testing proceeds to the comparison of voclosporin 23.7 mg BID versus Placebo treatment groups for the key secondary endpoints, then Hochberg testing procedure will be utilized. The p-values from the key secondary efficacy endpoints will be ordered from smallest to largest. The largest of these p-values will be compared to a significance level of 0.05. If the test rejects the null hypothesis of no treatment difference, then all p-values for the key secondary efficacy endpoints for voclosporin 23.7 mg BID versus Placebo treatment group will be declared statistically significant. If the largest p-value is not less than 0.05, then this p-value will not be declared statistically significant and testing will proceed to the next largest p-value.

If the largest p-value is not found to be statistically significant, then the second-largest p-value will be compared to a significance level of  $0.05/2 = 0.025$ . If this p-value is less than 0.025, then this p-value and the remaining p-values will be declared to be statistically significant. If the second largest p-value is not less than 0.025, then this p-value will not be declared to be statistically significant and testing will proceed to the third largest p-value.

If the second largest p-value is not found to be statistically significant, then the third largest p-value will be compared to a significance level of  $0.05/3 = 0.0167$ . If this p-value is less than 0.0167, then this p-value and the remaining p-values will be declared to be statistically significant. If the third largest p-value is not less than 0.0167, then this p-value will not be declared to be statistically significant and testing will proceed to the fourth largest p-value.

This process will continue until all p-values have been assessed as non-significant or significant.

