#### **13.8.4 Multiplicity**

An overall type 1 (false-positive) error rate of 5% for the efficacy endpoints will be maintained so that no statistical significance for the secondary efficacy endpoints will be claimed unless the principal analysis of the primary efficacy endpoint using the ITT set is statistically significant at the 5% level. The Hochberg step-up method will be used to adjust for multiple comparisons amongst key secondary endpoints and maintain the overall type 1 error rate [21]. Data from all analyses, regardless of the level of significance, will be presented for review.

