## 6.11 Efficacy Analyses

All statistical tests will be performed using a two-tailed 5% overall significance level, unless otherwise stated. All comparisons between treatments will be reported with 95% confidence intervals for the odds ratio, hazard ratio or difference as applicable.

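### Optional improvement: Hommel's procedure would reject everything that Hochberg rejects among the five key secondary tests, and occasionally more, at the same 5% level

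*SAP*

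**What the plan says.** Protocol 13.8.4 states: "The Hochberg step-up method will be used to adjust for multiple comparisons amongst key secondary endpoints". SAP 6.11.5 repeats the choice, saying that the step-up procedure "will be used to adjust for multiple comparisons amongst key secondary endpoints and maintain the overall type 1 error rate".

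SAP 6.11.5.1 sets the gate. The primary endpoint "will be tested first at a 0.05 significance level", and the key secondary endpoints are tested only if it succeeds.

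SAP 6.11.5.2 lists five key secondary comparisons: time to UPCR of 0.5 mg/mg or less, partial renal response at Week 52, partial renal response at Week 24, time to a 50% fall in UPCR, and adjudicated renal response at Week 24. If testing reaches the comparison of the arms "for the key secondary endpoints, then Hochberg testing procedure will be utilized". It then sets out the steps, beginning: "The largest of these p-values will be compared to a significance level of 0.05". The second and third largest p-values are compared with 0.025 and 0.0167, and so on down.

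Neither document mentions Hommel or gives a reason for preferring Hochberg. Neither states a power, an effect size or a correlation for any key secondary endpoint.

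**The concern.** Hochberg is a conservative short-cut to the closed test based on Simes; Hommel is that closed test carried out in full. The condition usually invoked for 5% control is the same for both, namely the Simes inequality. All five endpoints draw wholly or partly on the same UPCR measurements, so positive dependence is a natural working assumption. A plan that accepts Hochberg on that ground has in effect accepted what Hommel needs.

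At stake are the confirmatory claims beyond the primary endpoint, since these five comparisons are the only others under multiplicity control. When several p-values each lie just above their Hochberg cut-off, Hochberg may allow no claim where Hommel allows one or more.

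**Working it through.** **Inputs.** From the SAP: five tests (6.11.5.2), two-sided 5% (6.11), tested only after the primary succeeds (6.11.5.1). Assumed, because the documents give nothing: normal test statistics with a common pairwise correlation, and the mean z of each test.

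**The plan's own cut-offs.** Hochberg compares the k-th largest p-value with 0.05/k. For k = 1 to 5 this gives 0.05, 0.025, 0.0167, 0.0125 and 0.01. The three that the SAP writes out match.

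**Hommel's rule.** Order the p-values p(1) ≤ … ≤ p(5). Find the largest j for which p(5−j+k) > k × 0.05/j for every k = 1, …, j. If there is no such j, reject all five; otherwise reject every p ≤ 0.05/j.

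**Why Hommel never rejects less.** Suppose Hochberg stops at the r-th largest p-value, so that this p ≤ 0.05/r. For any j ≥ r it sits at position k = j − r + 1 among the j largest. Hommel's condition would need it to exceed 0.05(j − r + 1)/j. But (j − r + 1)/j ≥ 1/r whenever j ≥ r, since this rearranges to (r − 1)(j − r) ≥ 0. So every j ≥ r fails. Either no j qualifies and all five are rejected, or the qualifying j is below r, the cut-off 0.05/j exceeds 0.05/r, and this p-value and all smaller ones are rejected.

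**Winning all five.** Both procedures reject all five exactly when the largest p-value is at or below 0.05, so this probability is identical.

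**Illustration.** Take p = 0.0105, 0.013, 0.020, 0.030, 0.060.
- Hochberg: 0.060 > 0.05, 0.030 > 0.025, 0.020 > 0.0167, 0.013 > 0.0125, 0.0105 > 0.01. It rejects none.
- Hommel: j = 5 fails (0.013 is not above 0.02), j = 4 fails (0.020 is not above 0.025), and j = 3 fails (0.030 is not above 0.0333). j = 2 holds (0.030 > 0.025 and 0.060 > 0.05). The cut-off is 0.05/2 = 0.025, so three are rejected, with adjusted p-values 0.040, 0.040 and 0.045.

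A milder case is p = 0.011, 0.018, 0.029, 0.039, 0.051. Hochberg rejects none and Hommel rejects one (adjusted p 0.045).

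**Simulated power, each test at 80% marginal power** (mean z = 1.96 + 0.84 = 2.80; 500,000 trials per row; primary gate not modelled; Hochberg → Hommel):

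| Correlation | At least one rejected | Average share rejected | All five, both procedures | Trials where Hommel rejects more |
|---|---|---|---|---|
| 0 | 98.9% → 99.2% | 72.8% → 73.2% | 32.8% | 1.9% |
| 0.3 | 94.3% → 94.8% | 71.7% → 72.2% | 44.1% | 2.2% |
| 0.5 | 89.6% → 90.3% | 71.2% → 71.8% | 51.2% | 2.4% |
| 0.7 | 83.3% → 84.4% | 70.9% → 71.6% | 58.9% | 2.6% |
| 0.9 | 75.3% → 76.8% | 71.7% → 72.4% | 68.7% | 2.3% |

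**Wider range.** With a common mean z from 1.5 to 3.5 and correlation 0 to 0.7, Hommel rejects more in about 0.2% of trials (z 3.5, correlation 0) to 3.6% (z 2.0, correlation 0). Average power per endpoint rises by about 0.04 to 0.84 points. In no simulated trial did Hommel reject fewer.

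**Simulated family error with no true effect on any of the five** (Hochberg, Hommel): 4.86%, 4.89% at correlation 0; 4.24%, 4.36% at 0.5; 3.55%, 3.75% at 0.7; 2.66%, 2.95% at 0.9. Both stay below 5%.

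**The case against.** The strongest reply is that nothing here is wrong. Hochberg is valid under its usual condition, stated correctly, and identical in both documents. That stands: this is a choice between two acceptable procedures.

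The reply goes further, and most of it also stands.

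- **Hochberg has its own merits.** Its cut-offs are fixed and can be checked by eye. Because it rejects a subset of what Hommel rejects, it keeps slightly more error margin. Two-sided logistic and Cox tests on shared UPCR data have not been shown to meet the Simes condition exactly, so that margin has some value. A reader might infer that Hochberg buys nothing; that is too strong.
- **The first illustration is rare.** A reader might take it as the pattern to expect from five related UPCR endpoints. Four of its p-values lie only 0.0005 to 0.005 above their cut-offs, and the fifth lies 0.01 above. In simulation, Hochberg rejecting none while Hommel rejected three or more occurred in under 0.15% of trials for correlation up to 0.7, and in about 0.3% at 0.9.
- **The gate reduces the benefit.** With an assumed primary mean z of 2.8 and the same correlation, the share of trials with any gain becomes about 0.2% to 3.1% for correlation up to 0.7.
- **No promised power is lost.** The only power statement in either document (Protocol 13.2, SAP Section 4) concerns the primary endpoint, which this choice does not touch.

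None of this removes the basic point: if the Simes condition is accepted, Hommel is at least as powerful in every trial at the same error rate.

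**Conclusion.** This is a low-cost, optional improvement and not a defect. Under the condition normally cited for Hochberg, Hommel keeps 5% control and never rejects less. The expected benefit is below one percentage point of average power per endpoint. An extra claim appears in roughly 0.2% to 3.6% of trials, and the chance of winning all five does not change.

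These sizes rest on assumed equicorrelated normal statistics with a common mean. The documents supply no effect sizes or correlations for the key secondary endpoints, so no single value in the range can be preferred on their evidence. A reader might conclude that the family error rate is uncontrolled, or that the trial is materially underpowered for its key secondary claims. The documents support neither.

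**What to change.** If adopted, make the change before unblinding and in every place that names the procedure:

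1. In SAP 6.11.5, 6.11.5.1 and 6.11.5.2, replace Hochberg with Hommel at two-sided 5%, stating the rule given above. Editing only 6.11.5 and 6.11.5.2 would leave two procedures named for one family, because 6.11.5.1 also refers to Hochberg.
2. Replace Figure 6.1, whose title names Hochberg.
3. Report Hommel-adjusted p-values for the five comparisons.
4. Record the departure from Protocol 13.8.4 in SAP Section 9, which already lists changes to the key secondary family.
5. Leave the primary gate in 6.11.5.1 unchanged.

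The cost is SAP wording; standard software computes the adjustment, and no patients, data or extra alpha are needed. The drawbacks are a rule that is harder to describe and slightly less error margin should the Simes condition fail. If the sponsor values those more than the small gain, keeping Hochberg is defensible, and one sentence giving the reason would be enough.

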## 6.12 Pharmacokinetic Analyses

Estimates of voclosporin exposure derived from this analysis will be examined for possible relationship to measures of efficacy and safety. Full details will be described in a separate analysis plan.

## 6.13 Safety Analyses

The safety analyses will be presented by the treatment received. The following safety endpoints will be summarized;

- Biochemical (including liver function tests) and hematological laboratory tests
- AE profile and routine biochemical and hematological safety parameters
- Vital signs (BP, HR, temperature) at specific time points and change from baseline
- Standard 12-lead ECGs change from baseline
- Discontinuations from treatment
- Concomitant medications

### 6.13.1 Adverse Events

A treatment emergent adverse event (TEAE) is defined as:

- Any AE that has an onset on or after the first dose of study drug up to last dose + 30 days. For subjects consenting to the AURORA 2 continuation study there will be an additional constraint to the TEAE definition: events must have an onset date prior to the first dose of AURORA 2 study drug.

A treatment-related TEAE is defined as a TEAE that is assessed by the Investigator or Sponsor as being related to study drug. If a TEAE has a missing relationship to study drug it is assumed to be related to the study drug for analysis purposes.

A disease-related TEAE is defined as a TEAE that is assessed by the Investigator or Sponsor as being related to the disease under study. If a TEAE has a missing relationship to the disease under study it is assumed to be related to the disease under study for analysis purposes.

Missing severity assessments will be summarised as severe.

The following tables will be presented for AEs:

- Summary table of overall incidence, the number of events, risk difference and 95% CI (voclosporin-placebo) including the following top line summaries:
  - Any AE
  - Any TEAE
  - Any Treatment-Related TEAE
  - Any Serious TEAE
  - Any Treatment-Related Serious TEAE
  - Any TEAE Leading to Voclosporin/Placebo Discontinuation
  - Any TEAE Leading to Death
  - Treatment-Related TEAE Leading to Death
  - Disease-Related TEAE
  - Disease-Related Serious TEAE

Detailed list of AE tables is given at the end of this SAP.

In counting the number of AEs reported, a continuous event (i.e., reported more than once and which did not cease), will be counted only once for a subject; a non-continuous AE reported several times by the same subject will be counted as multiple events.

Additional tables for serious TEAEs will be provided for each of the four regions: North America, Latin America, Europe/South Africa and Asia Pacific. Similar tables will also be provided for serious TEAEs occurring between day 1 and day 84 (Up to week 12), day 85 to day 168 (Week 12 to 24) and greater than day 168 (after week 24).

All AEs will be listed and a glossary of unique verbatim terms with coding information will be provided.

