Procedures:	
See Schedule of Events for full details of protocol required procedures and applicable visits (and timings). Subjects who have provided signed and dated informed consent will be screened for entry into this study. Baseline proteinuria level is determined by a mean of 2 first morning void urine samples taken during the screening period. If a subject has not had a kidney biopsy within the required timeframe for study eligibility, one may be performed to assess eligibility into the study, provided consent is in place and provided the results are received before randomization. Subjects meeting the required eligibility criteria will be randomized in a ratio of 1:1 to receive either Orelvo (23.7 mg BID) or matching placebo starting on Day 1. All subjects will receive initial treatment with 0.5 to 1.0 g IV methylprednisolone. In consultation with the Medical Monitor, and if it is in the subject's best interest, IV methylprednisolone may be started during the screening period. Subjects receiving IV methylprednisolone in the 3 months prior to screening must be discussed with the Medical Monitor prior to initiating further IV methylprednisolone. For subjects who are not already taking prescribed MMF prior to randomization, the dosing of MMF will start at 500 mg BID for a total daily dose of 1 g/day for the first week, increasing to 1 g BID for a total daily dose of 2 g/day for the second and subsequent weeks (i.e., beginning on Day 8).
 
All subjects will complete dosing through 52 weeks of study treatment. Subjects who permanently discontinue study treatment before the Week 52 visit will return for all remaining study visits and assessments unless they have withdrawn consent. All subjects who complete participation and study treatment through 52 weeks and provide consent will have the opportunity to enroll into a continuation study for which the details are not yet finalized.

Sample Size:	
A 2 group continuity corrected Chi square test with a 0.05 two-sided significance level will have 80% power to detect the difference between a placebo response rate of 20.0% and an Orelvo response rate of 34.4% (odds ratio=2.1) when the sample size in each group is 162 (total N=324). While the effect of withdrawals will be investigated, subjects withdrawing for any reason will be counted as non-responders in the primary analysis and therefore no adjustment of sample size for withdrawals is necessary.

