### **1.2.5 Potential Toxicities**

Voclosporin has been studied in numerous disease states. When examining LN, there were a small proportion of voclosporin treated subjects that experienced an early drop of  $\geq 30\%$  in eGFR, however that proportion then remains stable over time. None of these treatment-emergent adverse events (TEAEs) were classed as serious. The majority of TEAEs of decreased GFR were classed as mild or moderate, and resulted in permanent discontinuation of study drug in 1 (1.1%) placebo subject, 6 (6.7%) voclosporin low-dose subjects and 5 (5.6%) voclosporin high-dose subjects. There were more TEAEs of hypertension seen in the voclosporin-treated patients compared to placebo however, overall mean systolic and diastolic blood pressure (BP) decreased in all groups, without statistically significant differences seen between groups. Overall, only 1 (1.1%) subject, in the voclosporin high-dose group, had a TEAE of hypertension that resulted in permanent discontinuation of study drug.

There was evidence of an increased incidence of TEAEs over placebo and with increased dose of voclosporin in the System Organ Classes of Infections and Infestations, Gastrointestinal Disorders, and Vascular Disorders.

There were more deaths in the voclosporin low-dose arm (10) than in either the voclosporin high-dose (2) or placebo (1) arms, with the majority (11/13) occurring in South-East Asia. All deaths were assessed by the Investigator and Data and Safety Monitoring Board (DSMB) as unrelated to study treatment. A full description of adverse events can be found in the IB.

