### **5.6.1 Discontinuation from Study Treatment Due to Early Non-response to Therapy**

Subjects will be discontinued from study treatment if their early disease response is suboptimal. The Investigator must contact the Medical Monitor to discuss further continuation in the study if the subject meets 1 of the 2 following criteria:

- After 12 weeks of treatment, the subject shows a >30% decrease from baseline value in CKD-EPI eGFR in 2 successive measurements separated by at least 4 weeks

or

- After 8 weeks of treatment, the subject shows a confirmed reduction in UPCR of  $\leq 25\%$  assessed by 2 consecutive measurements at least 2 weeks apart.

If the subjects require treatment with IV methylprednisolone or any rescue medication other than that permitted in the protocol (see Section 7.2.2.2, [Corticosteroids](#)), they should be permanently discontinued from the study treatment and will be considered a treatment failure. Subjects who are permanently discontinued from study treatment will be treated as deemed appropriate by the Investigator.

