### **13.9 Safety Evaluations**

Specific safety endpoints are as follows:

- Biochemical (including liver function tests) and hematological laboratory tests
- AE profile and routine biochemical and hematological safety parameters
- Vital signs (BP, HR, temperature) at specific time points and change from baseline
- Standard 12-lead ECGs change from baseline
- Discontinuations from treatment
- Concomitant medications

Laboratory values, vital signs, and other safety parameters providing numeric data will be summarized by treatment arm, visit, and as change from baseline.

Adverse events will be coded using the latest available version of the Medical Dictionary for Regulatory Activities, the version of which will be provided in the clinical study report.

Treatment-emergent adverse events will be summarized by treatment arm, system organ class, and preferred term. SAEs, SAEs that led to death, and SAEs/AEs that led to withdrawal will also be summarized and listed.

Only AEs which started on or after the date of first dose of study treatment will be considered TEAEs, though all AEs after informed consent will be recorded. SAEs occurring at any time after informed consent will be summarized. All concomitant medications will be summarized.

Details of these and other analyses will be provided in the SAP.

All study data analyses involving laboratory values will be based on results from the central laboratory.

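### The overall AE summary in SAP 6.13.1 compares the arms on death only through treatment-emergent events, so an on-study death from an event starting more than 30 days after last dose falls outside that comparison

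*SAP*

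**What the plan says.** SAP 6.13.1 describes the table as "Summary table of overall incidence, the number of events, risk difference and 95% CI (voclosporin-placebo) including the following top line summaries". The rows that follow include one unrestricted row for any AE. Death appears only as "Any TEAE Leading to Death" and as the treatment-related version of the same row. The same section defines a TEAE as "Any AE that has an onset on or after the first dose of study drug up to last dose + 30 days", and for subjects who continue into AURORA 2 the onset must also precede the first dose in that study. The limit is therefore on when the event began, not on the date of death.

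Other parts of the plan use wider periods:

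- **Protocol 13.9:** "Only AEs which started on or after the date of first dose of study treatment will be considered TEAEs". No end of the window is given. The same section says "SAEs occurring at any time after informed consent will be summarized" and also plans a summary and listing of SAEs that led to death.
- **Protocol Synopsis:** "Subjects who permanently discontinue study treatment before the Week 52 visit will return for all remaining study visits and assessments", unless consent is withdrawn.
- **Protocol 10.3.2:** deaths are reportable during the study and up to 30 days after the last study visit or last dose, whichever is longer.
- **SAP 3.1:** death at any time before the 1-year assessment counts as non-response.

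The SAP's amendment history records the last dose + 30 days limit as a version 5.0 change (October 2019). SAP section 9, which lists changes from the protocol's planned analysis, does not mention it.

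**The concern.** The design creates off-drug time on study. Protocol 5.6.1 states: "Subjects will be discontinued from study treatment if their early disease response is suboptimal", with criteria that apply after 8 or 12 weeks of treatment. Subjects may also stop for adverse events or falls in eGFR. These reasons are informative and may differ by arm. In Phase 2, decreased GFR led to permanent discontinuation in 6 low-dose, 5 high-dose and 1 placebo subjects (Protocol 1.2.5).

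Mortality deserves a clean comparison in this trial. Phase 2 had 10 deaths at low dose, 2 at high dose and 1 on placebo, and the low dose, 23.7 mg BID, is the dose now tested. With few deaths expected, moving even a few in or out of the count can change a risk difference and its interval. As written, the death rows with a between-arm comparison depend partly on when each subject stopped drug.

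**Working it through.** **1. Phase 2 figure.** 10 + 2 + 1 = 13 deaths; 13/265 = 4.9%, as Protocol 1.2.4.2 states.

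**2. Follow-up outside the window.** For a subject who stops drug at week w and stays to Week 52 (364 days), the days on which a new fatal event would not be a TEAE are 364 − 7w − 30.

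| Drug stopped at | Days outside window before Week 52 | Share of 364 days |
|---|---|---|
| Week 8 | 364 − 56 − 30 = 278 | 76% |
| Week 12 | 364 − 84 − 30 = 250 | 69% |
| Week 24 | 364 − 168 − 30 = 166 | 46% |
| Week 36 | 364 − 252 − 30 = 82 | 23% |

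This step uses only the documents' own rules.

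**3. Share of on-study deaths outside the window (illustrative).** The documents give no stopping rate or off-drug hazard for this trial. Assume that a fraction d of subjects stops at Week 26 on average, that all of them stay to Week 52, that the off-drug hazard is h times the on-drug hazard, and that death coincides with event onset. Thirty days is 4.3 weeks, so each stopper has 26 − 4.3 = 21.7 weeks outside the window.

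Share = h·d·21.7 / (h·d·21.7 + 52 − d·21.7)

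- d = 0.15, h = 1: 3.255 / (3.255 + 52 − 3.255) = 0.063
- d = 0.35, h = 3: 22.785 / (22.785 + 52 − 7.595) = 0.339

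The range is 6% to 34%. It is a pooled share and says nothing about a difference between arms.

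**4. Sensitivity of a small death count (illustrative).** Phase 2 arm sizes are not stated. The adverse event percentages in Protocol 1.2.4.2 and 1.2.5, with the total of 265, point to 89 low dose, 88 high dose and 88 placebo. The placebo SAE figure of 15.8% was set aside, because 14/88 is 15.9%. On those sizes, 10/89 (11.2%) v 1/88 (1.1%) gives a risk difference of 10.1 points (Wald 95% CI 3.2 to 17.0; Fisher p = 0.009).

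If those rates recurred at 162 per arm, deaths would be about 10/89 × 162 = 18 v 1/88 × 162 = 2. Removing deaths from the voclosporin arm only, which is the most one-sided case:

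| Deaths counted | Risk difference, points (95% CI) | Fisher p |
|---|---|---|
| 18 v 2 (all) | 9.9 (4.7 to 15.0) | 0.0003 |
| 14 v 2 (4 outside window) | 7.4 (2.8 to 12.1) | 0.003 |
| 9 v 2 (9 outside window) | 4.3 (0.4 to 8.2) | 0.06 |

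This shows how sensitive a sparse comparison can be. It is not a forecast.

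**The case against.** The strongest reply is that these deaths are already covered. Protocol 13.9 plans a summary and listing of SAEs that led to death, a fatal event is an SAE by definition, the SAP lists all AEs, and SAP section 9 withdraws none of this. SAP 6.13.1 also refers to a detailed table list at the end of the document, and only the heading of section 11 was available. All of that stands. A reader might infer that off-drug deaths go unreported, or that no all-deaths table exists; the documents support neither. What remains is narrower: in the SAP text that can be read, no risk difference with 95% CI is attached to a count of all deaths. The protocol's SAE outputs may not fill that gap, because Protocol 10.3.2 can be read as ending SAE reporting 30 days after last dose for subjects who discontinue, while its death-reporting period runs longer. Those two periods should be reconciled.

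A reader might also take every death during off-drug follow-up to be excluded. That is too broad: a late death still counts if the fatal event began by last dose + 30 days.

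Nor does the Phase 2 imbalance show that such a window would hide deaths. The documents do not say how many of those deaths were off drug, and all were assessed as unrelated to study treatment. The imbalance is a reason to look closely at mortality and nothing more.

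Finally, the 6% to 34% range rests on assumed inputs. Two of them push it up: that all stoppers remain to Week 52, and that onset and death coincide. It shows no distortion between arms.

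**Conclusion.** The point holds in a limited form. The death rows stated to carry the arm comparison are restricted to events starting by last dose + 30 days, while follow-up, death reporting and the primary estimand all extend further. The protocol's TEAE definition has no such end, and SAP section 9 does not declare the narrowing. That much follows from the text alone.

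The effect on the risk difference cannot be derived, because stopping rates, off-drug hazards and deaths in this trial are not in the documents. The 6% to 34% share and the 162-per-arm illustration are conditional on the assumptions shown, and neither demonstrates bias in either direction. The case for change is that a headline mortality contrast should not depend on when drug was stopped, and that removing this dependence is cheap.

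**What to change.** 1. Keep the TEAE death rows in the SAP 6.13.1 overall summary and add a row, 'Any death on study', with the same risk difference and 95% CI.
2. Define it as all deaths from first dose to the end of the death-reporting period in Protocol 10.3.2 and, for subjects who continue, before the first AURORA 2 dose. Count them whatever the last dose date or the onset of the fatal event.
3. Use the Safety population by treatment received, as for the rest of the table. A count from first dose by randomised arm would match neither the Safety nor the ITT population, and an end point of last contact could run into AURORA 2.
4. State the last dose + 30 days window in SAP section 9 as a change from Protocol 13.9.

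If section 11 already contains an all-deaths comparison with a risk difference and CI, a cross-reference from 6.13.1 would replace items 1 to 3, provided that its population and end date match. The cost is one table row and one sentence in section 9. No new data are needed, since deaths are already reportable over this period.
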